***Cohort 1 and Cohort J1 Allowable PK Windows**

On Days 1, 15, and 85 and at Weeks 16, 24, and 36, the PK samples collected prior to infusion should be collected within 30 minutes of the start of infusion. For 1-hour post-dose samples (Days 1, 15, and 85), the allowable PK window is ± 6 minutes, and for 2-hour post-dose samples (Days 1, 15, and 85), the allowable PK window is ± 12 minutes. The allowable window is ± 2 days for samples scheduled on Days 5, 89, and 99, and ± 4 days for samples scheduled on other study days.

For Subjects Enrolled in Cohort 2 (*See Below for Allowable PK Windows)

- **Days 1, 29, 85, and Weeks 24 and 36 (Doses 1, 3, 5, 8, and 11, respectively)**
 - Prior to the start of the infusion (0 hour, no more than 30 minutes prior to the start of the infusion).
- **Day 15 (Dose 2)**
 - Prior to the start of the infusion (0 hour, no more than 30 minutes prior to the start of the infusion), immediately after the end of the infusion (within 15 minutes) and 1 and 2 hours after the end of the infusion.

- **Week 52: (Study Completion/Premature Discontinuation Visit)**
 - Sample may be collected anytime during the day.
- **Weeks 60 and 68 (Post-Treatment Follow-up Period)**
 - Sample may be collected anytime during the day.

***Cohort 2 Allowable PK Windows**

On Days 1, 15, 29, and 85 and at Weeks 24 and 36, the PK samples collected prior to infusion should be collected within 30 minutes of the start of infusion. For 1-hour post-dose sample (Day 15), the allowable PK window is ± 6 minutes, and for 2-hour post-dose samples (Day 15), the allowable PK window is ± 12 minutes. For the samples scheduled for Weeks 52, 60, and 68, the allowable window is ± 4 days.

Blood Samples for ABBV-8E12 Anti-Drug Antibodies (ADA) Assays

Blood samples, approximately 3 mL for ABBV-8E12 ADA analysis will be collected by venipuncture. The collection schedule for ADA will be the same for subjects who previously did or did not participate in the Single-Ascending Dose Study (Study C₂N-8E12-WW-104). The schedule for ABBV-8E12 ADA collection is as follows:

For Subjects Enrolled in Cohort 1 and Cohort J1 (*See Below for Allowable ADA Windows)

- **Days 1, 15, 29, 57, 85, and Weeks 16, 24, and 36 (Doses 1, 2, 3, 4, 5, 6, 8, and 11, respectively)**
 - Prior to the start of the infusion (0 hour, no more than 30 minutes prior to the start of the infusion).
- **Days 89 and 99**
 - Sample may be collected anytime during the day.
- **Week 52: (Study Completion/Premature Discontinuation Visit)**
 - Sample may be collected anytime during the day.
- **Weeks 60 and 68: Post-Treatment Follow-up Period**

- Sample may be collected anytime during the day.

***Cohort 1 and Cohort J1 Allowable ADA Windows**

On Days 1, 15, 29, 57, 85, and Weeks 16, 24, and 36, the ADA samples collected prior to infusion should be collected within 30 minutes of the start of infusion. Blood samples may be collected within ± 2 days on Days 89, and 99, and ± 4 days on other study days.

For Subjects Enrolled in Cohort 2 (*See Below for Allowable ADA Windows)

- **Days 1, 29, 85, and Weeks 24 and 36 (Doses 1, 3, 5, 8, and 11, respectively)**
 - Prior to the start of the infusion (0 hour, no more than 30 minutes prior to the start of the infusion).
- **Week 52: (Study Completion/Premature Discontinuation Visit)**
 - Sample may be collected anytime during the day.
- **Weeks 60 and 68: Post-Treatment Follow-up Period**
 - Sample may be collected anytime during the day.

***Cohort 2 Allowable ADA Windows**

On Days 1, 29, 85, and Weeks 24, and 36, the ADA samples collected prior to infusion should be collected within 30 minutes of the start of infusion. Blood samples may be collected within ± 4 days on other study days.

CSF Samples for ABBV-8E12 Assay

CSF samples will be collected as outlined in the Study Activities Table ([Appendix C-Assessment](#) referred to as LP).

The collection time and procedures of CSF samples can be found in the Lumbar Puncture section of Study Procedures Section (Section 5.3.1.1).

As described in the Collection and Handling of Biomarker and Pharmacogenetic Research Samples Section (Section 5.3.1.2), CSF samples (18 – 20 mL) will be collected by lumbar puncture.

5.3.2.2 Measurement Methods

Analysis of Serum and CSF Samples

Serum concentrations and relative titers of ABBV-8E12 ADA will be determined using validated methods at the Bioanalysis Department at AbbVie. CSF concentrations of ABBV-8E12 will be analyzed using qualified or validated methods. Any additional analytes may be analyzed using non-validated methods either at AbbVie or by outside vendors or collaborators. Serum samples collected for ABBV-8E12 and ABBV-8E12 ADA analysis may be used for future assay development or validation activities. ABBV-8E12 ADA samples may be used for the analysis of neutralizing anti-drug antibodies.

5.3.3 Efficacy Variables

The primary efficacy variable will be the mean change from Baseline at Day 1 pre-dose to the Week 52 assessment in the PSP Rating Scale (PSPRS) total score to assess the effect of ABBV-8E12 in slowing disease progression.

- Secondary efficacy measures include the SEADL, UPDRS Part II, CGI-S, CGI-C, and PSP-QoL, and PSP Staging System and time to loss of ability to walk independently as measured by PSPRS item 26, as well as regional (midbrain, third ventricle, frontal lobes, superior cerebellar peduncle, brainstem) and whole brain atrophy as measured by volumetric MRI.
- Exploratory efficacy variables include the RBANS, Color Trails Test (Parts 1 and 2), Letter Fluency Test, NNIPPS-PPS, PGI-C, and EuroQoL-5D (EQ-5D). Exploratory quantitative MRI measures may additionally be evaluated; including diffusion tensor imaging (DTI), derived fractional anisotropy (FA) and diffusivity measures [radial diffusivity (RD), mean diffusivity (MD), and

axial diffusivity] to assess changes in pathophysiology and additional regions as measured by volumetric MRI.

Analysis of the secondary and exploratory efficacy variables obtained from these measures is detailed in Section 8.0.

5.3.4 Safety Variables

The following safety evaluations will be performed during the study: adverse event monitoring (including infusion and allergic reactions), vital signs, physical examination, complete neurological exam, cognitive assessments, C-SSRS, laboratory abnormalities, ECG, MRI including FLAIR, and immunogenicity as determined by ADA responses in blood.

5.3.5 Pharmacokinetic Variables

Values for the following pharmacokinetic parameters will be estimated using non-compartmental methods: maximum observed serum concentration (C_{max}), the time to C_{max} (peak time, T_{max}), the area under the concentration time curve (AUC) over the dosing interval after the first and the fifth doses in Cohort 1 and Cohort J1; and the observed serum concentration at the end of a dose interval (C_{trough} , concentration prior to infusion on a day of dosing) in both Cohort 1, Cohort J1, and Cohort 2.

The concentration of ABBV-8E12 in CSF will be summarized after the fifth dose and after the final dose if administered at least 3 months after the previous LP for subjects in Cohort 1 and Cohort J1, and after final dose for subjects in Cohort 2.

A mixed-effect modeling approach will be used to estimate the population central value and the empirical Bayesian estimates of the individual values for ABBV-8E12 clearance (CL) and volume of distribution (V).

Additional parameters may be calculated if useful in the interpretation of the data.

5.3.6 Biomarker and Pharmacogenetic Research Variables

5.3.6.1 Biomarker Research Variables

Blood and CSF samples will be collected to conduct research to investigate disease-related and drug-related biomarkers. The biomarkers to be analyzed may include, but are not limited to, the following:

- CSF and plasma samples will be assayed for tau to demonstrate tau binding of ABBV-8E12 and for neurofilament to examine effects on neurodegeneration.
- CSF or plasma samples may be analyzed for biochemical or macromolecular factors related to the pharmacodynamics and safety of ABBV-8E12.

Exploratory evaluations from blood and CSF samples may include analyzing biomarkers related to the pathway(s) targeted by the study drug or believed to be related to the disease or to drug response.

The information learned from analyzing these data may be used to investigate factors impacting response to treatment, scientific questions related to PSP, support development of ABBV-8E12, or in the development of new therapies. Furthermore, given the exploratory nature of these data the results may not be included in the study summary.

5.3.6.2 Pharmacogenetic Research Variables

MAPT H1/H2 haplotype status may be determined for each subject and analyzed as a factor contributing to the subject's response to study treatment. The MAPT H1/H2 haplotype results may be analyzed as part of a multi-study assessment of MAPT and response to ABBV-8E12 treatment. Testing for GRN haploinsufficiency polymorphisms will also be conducted as patients with these mutations typically have low progranulin serum levels and are less likely to have tau brain pathology. The results may also be used for the development of diagnostic tests related to ABBV-8E12, or other drugs in development for PSP or related conditions. The MAPT haplotype and progranulin results may not be included in the study summary.

Optional samples may be collected to conduct exploratory investigations into known and novel biomarkers. The types of biomarkers to be analyzed may include, but are not limited to, nucleic acids, proteins, lipids or metabolites. The samples may be analyzed as part of a multi-study assessment of factors influencing the subjects' response to the study drug (or drugs of the same or similar class) or the development and progression of the subjects' disease or related conditions. The samples may also be used to develop new diagnostic tests, therapies, research methods or technologies. The results from these analyses are exploratory in nature and may not be included with the study report.

5.3.7 Immunogenicity

ADA levels will be determined for the assessment of immunogenicity.

5.4 Removal of Subjects from Therapy or Assessment

5.4.1 Discontinuation of Individual Subjects

Each subject has the right to withdraw from the study at any time. In addition, the investigator may discontinue a subject from the study at any time if the investigator considers it necessary for any reason, including the occurrence of an adverse event or noncompliance with the protocol.

Severe allergic reactions or other adverse events that require the immediate interruption of ABBV-8E12 treatment will be taken into consideration by the AbbVie Medical Director for permanent discontinuation from further treatment and initiation of appropriate medical therapy and follow-up.

Any treatment-emergent, clinically significant, symptomatic neurological abnormalities and treatment-emergent MRI findings will be reported to the AbbVie Medical Director and subjects will be considered for discontinuation from treatment if clinically indicated.

Subjects at risk of suicide as indicated by answering yes to question 4 or 5 on the C-SSRS and/or determined by the investigator to be at risk of suicide, should be promptly referred

for appropriate follow-up care. Subjects determined to be at ongoing risk of suicide should be discontinued from study participation.

If for any reason the subject becomes unable to continue treatment with ABBV-8E12, undergo protocol required procedures, or otherwise continue to participate in the study, discontinuation should be discussed with the AbbVie Medical Director.

In the event that a subject withdraws or is discontinued from the study, the primary reason for discontinuation and any other reason(s) for the discontinuation from the study will be recorded and a physical examination, neurological examination, body weight, vital signs measurement, ECG, laboratory analyses, MRI, LP, administration and completion of scales/questionnaires, C-SSRS and an assessment of adverse events and concomitant medications will be performed as soon as possible after discontinuation from the study (Refer to Study Activities Table, [Appendix C](#)). Additional blood samples for drug measurement may be collected at the time of discontinuation from subjects who are discontinued due to adverse events; the clock time, time in relation to dose and date the sample was taken will be recorded.

If a subject is discontinued from the study with an ongoing adverse event or an unresolved laboratory result that is significantly outside of the reference range, the investigator will attempt to provide follow-up until a satisfactory clinical resolution of the laboratory result or adverse event is achieved.

In the event that a positive result is obtained on a pregnancy test for a subject or a subject reports becoming pregnant during the study, the administration of study drug to that subject must be discontinued immediately. The investigator must report a pregnancy within 1 working day of the site being aware to one of the AbbVie representatives listed in Section [6.1.5](#) or Section [7.0](#).

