5.6 Discussion and Justification of Study Design

5.6.1 Discussion of Study Design and Choice of Control Groups

This study is designed to assess the efficacy, safety, and tolerability of ABBV-8E12 in subjects with PSP for up to 52 weeks. The inclusion of placebo administration and the double blind nature of the study will provide unbiased assessments. The parallel-group design with placebo control will provide a well-controlled unbiased assessment of the effect of ABBV-8E12 on clinical outcome measures and potential neuroimaging and CSF

biomarkers that are associated with PSP disease activity. Toxicity management in the parallel group design is described in Section 6.1.7.

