6.1.2 Adverse Event Severity

The investigator will use the following definitions to rate the severity of each adverse event:

Mild	The adverse event is transient and easily tolerated by the subject.
Moderate	The adverse event causes the subject discomfort and interrupts the subject's usual activities.
Severe	The adverse event causes considerable interference with the subject's usual activities and may be incapacitating or life-threatening.

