Subjects will be closely monitored for treatment-related adverse events, including allergic reactions, during the infusion. For their first 4 ABBV-8E12 infusions, subjects should be monitored on site until 2 hours post-infusion. For subsequent infusions, subjects should be monitored on site until at least 30 minutes after the end of infusion. Subjects in Cohort J1 will be confined for a minimum of 24 hours following their first infusion. The Investigator will assess safety 2 days after the first infusion, either while in hospital or as an outpatient. From their second to fourth infusion, Cohort J1 subjects will be observed

on-site for at least 2 hours following each infusion of study drug. Subjects in Cohort 2 will be observed on-site for at least 2 hours following each of the first 4 infusions of study drug. Following the 4th infusion, all subjects should be monitored on-site for at least 30 minutes after the end of infusion. Longer observation periods and more frequent vital sign checks may be required in subjects who experience infusion reactions. In general, Infusion reactions are more frequently observed during the first infusion and within 24 hours from the start of administration, especially within the first 2 hours.²⁹ Please refer to [Table 2](#), Safety Observation Period Following Infusions, for a summary of the observation periods following infusions.

Severe or life-threatening allergic reactions require the immediate interruption of ABBV-8E12 treatment and permanent discontinuation from further treatment. Appropriate medical therapy including epinephrine, corticosteroids, intravenous antihistamines, bronchodilators, and oxygen should be available for use in the treatment of such reactions. Subjects should be carefully observed until the complete resolution of all signs and symptoms.

Moderate infusion reactions resolving with supportive care should be discussed with the TA MD, and a reduction of the infusion rate for future administrations can be considered.

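### The protocol makes permanent discontinuation mandatory after a severe allergic reaction in Section 6.1.7 but leaves it to the sponsor's Medical Director in Section 5.4.1

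*Protocol*

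**What the plan says.** Protocol Section 5.4.1 (Discontinuation of Individual Subjects) states: "Severe allergic reactions or other adverse events that require the immediate interruption of ABBV-8E12 treatment will be taken into consideration by the AbbVie Medical Director". The outcome is worded as a referral: such events "will be taken into consideration by the AbbVie Medical Director for permanent discontinuation from further treatment", together with medical therapy and follow-up.

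Protocol Section 6.1.7 (Toxicity Management), under Allergic Reactions Management, states: "Severe or life-threatening allergic reactions require the immediate interruption of ABBV-8E12 treatment and permanent discontinuation from further treatment". The next paragraph provides for discussion with the sponsor's physician, but only at a lower grade: "Moderate infusion reactions resolving with supportive care should be discussed with the TA MD".

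Section 6.1.2 defines the severe grade for the whole protocol: "The adverse event causes considerable interference with the subject's usual activities and may be incapacitating or life-threatening". Section 5.6.1 directs the reader to one of the two sections: "Toxicity management in the parallel group design is described in Section 6.1.7". The SAP sets no discontinuation rule for allergic reactions.

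**The concern.** A subject who has a severe allergic reaction must stop permanently under one section. Under the other, that subject is a case for the Medical Director to weigh. Sections 5.4.1 and 6.1.7 do not refer to each other on this point.

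The rule decides whether a subject is re-exposed to an infused antibody after a severe reaction. Section 6.1.7 itself lists allergic and infusion reactions, including anaphylaxis, among the potential toxicities. A site working from Section 6.1.7 stops treatment for good. A site working from Section 5.4.1 refers the case and waits, and the answer may be further dosing that Section 6.1.7 does not allow.

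There is a secondary effect on the data. The decision sets the last-dose date, which starts the 45-day limit on efficacy data (Protocol 8.1.3, SAP 10.1). It also decides who is counted as discontinuing study drug (SAP 8.0) and who appears in the tables of adverse events leading to discontinuation (SAP 11.2.2).

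**Working it through.** There is no figure in the plan to reproduce. The check is a comparison of the two rules, followed by simple counts for scale.

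**Side by side**

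| | Section 5.4.1 | Section 6.1.7 |
|---|---|---|
| Grade covered | Severe | Severe or life-threatening |
| Condition | Reaction requires immediate interruption | None beyond the grade |
| Permanent stop | Considered by the Medical Director | Required |
| Discussion with sponsor physician | At the severe grade | At the moderate grade only |

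**Do they cover the same event?**

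1. Grade. Section 6.1.2 has three grades: mild, moderate and severe. Its severe grade includes life-threatening events, so both sections reach the same top grade.
2. Condition. Section 5.4.1 applies to reactions that require immediate interruption. Section 6.1.7 says every severe allergic reaction requires it. Every event under the Section 6.1.7 rule therefore also meets the Section 5.4.1 condition.
3. Relatedness. Section 6.1.7 introduces its rules as guidance for drug-related toxicity. Section 5.4.1 has no such limit. The overlap is therefore certain for drug-related severe reactions.

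**Does any text settle precedence?** Section 5.6.1 points to Section 6.1.7 for toxicity management without saying that it overrides Section 5.4.1. Section 6.1.6 points to Section 5.4.1 for stopping study drug in pregnancy, so Section 5.4.1 is also an operative section. The pregnancy rule is a useful contrast: Sections 5.4.1 and 6.1.6 both make stopping mandatory, and the second cross-refers to the first. The allergic-reaction rule has neither the match nor the cross-reference.

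**Scale** (Protocol Table 3: 14 infusions, 110 subjects per arm)

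- Active infusions, if all complete: 14 × (110 + 110) = 3,080.
- Infusions at which blinded sites must be ready to apply the rule: 14 × 330 = 4,620.

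Both are upper limits on occasions, not counts of events.

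**Effect on one subject's data.** Take a severe reaction at dose 5 (Day 85). If treatment stops, efficacy data count up to Day 85 + 45 = Day 130, so a PSPRS at the scheduled Week 24 date (Day 169) would fall outside the limit. If dosing resumes and runs to dose 14 (Day 337), the limit is Day 337 + 45 = Day 382, and the nominal Week 52 assessment (Day 52 × 7 + 1 = 365) counts.

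**The case against.** The strongest reply is that this is loose wording, not two instructions that cannot both be obeyed. A site that stops treatment under Section 6.1.7 breaches nothing in Section 5.4.1, which can be read as describing the Medical Director's part in the process. The acute step is the same in both sections. Under Section 5.4.1 the decision belongs to the sponsor, so re-dosing would need a central decision against the express text of Section 6.1.7. The protocol also sends readers to Section 6.1.7 for toxicity management, and that section is framed around drug-related events.

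Events are also likely to be rare. The introduction reports no systemic hypersensitivity reaction in the single-dose study, and Section 6.1.7 reports no infusion reactions in that study or in the expanded-access use. The infusion counts assume that everyone completes, whereas SAP 4.3 assumes 25% without Week 52 data.

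Much of this stands. Any divergence comes from which section a site follows, not from sites making the final decision themselves. The effect on the efficacy estimate is probably small, and none has been shown for the primary result. The relatedness point limits the certain overlap to drug-related reactions. Earlier exposure was small, however: 23 subjects with single doses and two with repeated doses (Section 3.2).

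None of it removes the conflict. For a drug-related severe reaction, a permanent stop cannot be both required and a matter for consideration. A pointer to Section 6.1.7 is not a statement that it prevails.

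**Conclusion.** The concern holds. The protocol gives two different outcomes for a severe allergic reaction, without a precedence clause or a cross-reference. This is an internal contradiction in a stopping rule. It is certain for drug-related reactions; for reactions with another cause it depends on how the framing of Section 6.1.7 is read.

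The number of subjects affected cannot be estimated, because the documents give no event rate; it is probably low. The case for correction rests on patient safety. The consequences for disposition counts and the 45-day cut-off are real for each subject affected but likely minor overall. Given what each such decision means for the subject, it should be corrected and not left to interpretation. No view is taken here on which rule is clinically right.

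**What to change.** Reconcile Sections 5.4.1 and 6.1.7 so that both state one identical rule for severe and for life-threatening allergic reactions, each citing the other. The text should say whether the rule depends on relatedness to study drug. The sponsor's clinical team must choose the rule.

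In the same edit, check the reference in Section 5.4.1 to other adverse events against Section 6.1.7.1. That section requires discontinuation after severe or life-threatening drug-related nervous-system events, so the same sentence may create a second mismatch.

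The text change is about one sentence, with a site notice. The process costs more than the wording: Section 9.1 calls for ethics approval of amendments, there are about 60 sites, and the country-specific versions must be kept aligned. Sample size, analysis methods and the SAP do not change.
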